### 7.1 Adverse Event

For the purposes of this study, an adverse event (AE) is any untoward medical occurrence, unintended disease or injury, or untoward clinical signs in subjects, whether or not related to the investigational device or procedure. In addition, the definition of AE applies to any event with an onset during enrollment / index procedure or to any underlying diseases, present at baseline, that exacerbate in severity post study procedure. Therefore, an underlying disease that was present at the time of enrollment is not reported as an AE, but any increase in the severity of the underlying disease is to be reported as an AE. This definition includes events occurring during the follow-up period.

All reported AEs through 12 months must be recorded in the electronic database. Following the 12-month visit, only SAEs and UADEs will be recorded in the electronic database. A description of the event, including the start date, resolution date (or final outcome assessment date), action taken, and the outcome should be provided, along with the Investigator's assessment of the severity, seriousness, the relationship between the AE, the study device and the study procedure.

The following definitions for rating severity of adverse events will be used:

- Mild: Awareness of signs or symptoms, but easily tolerated; are of minor irritant type; causing no loss of time from normal activities; symptoms would generally not require medication or a medical evaluation; signs or symptoms are transient (e.g., headache treated with acetaminophen, common cold, etc. would be considered mild).
- Moderate: Interferes with the subject's usual activity and/or requires symptomatic treatment.
- Severe: Symptom(s) causing severe discomfort and significant impact of the subject's usual activity and requires treatment.

**Adverse Device Effect (ADE) / Device-Related Adverse Event:** an adverse device effect (or device-related adverse event) is defined as any untoward adverse effect when, in the judgment of the Investigator, the clinical event has a reasonable time sequence associated with use of the assigned device (e.g., WRAPSODY Endovascular Stent Graft System or standard PTA) and is unlikely to be attributed to concurrent disease or other procedures or medications. It is reasonable to believe that the device directly caused or contributed to the adverse event. A Serious Adverse Device Effect (SADE) is an event that also meets at least one of the seriousness definitions as listed in Section 7.2.

NOTE 1: This definition includes adverse events resulting from insufficient or inadequate Instructions for Use, deployment, implantation, installation, or operation, or any malfunction of the investigational medical device.

NOTE 2: This definition includes any event resulting from user error or from intentional misuse of the investigational medical device.

**Procedure-Related Adverse Event:** an adverse event is considered to be procedure-related when, in the judgment of the Investigator, it is reasonable to believe that the event is associated with the assigned study procedure and is not specific to the assigned device (e.g., WRAPSODY Endovascular Stent Graft System or standard PTA) used. Other products, surgical techniques, or medications required specifically for the procedure are likely to have contributed to the occurrence of the event.

**Concomitant Medication-Related Adverse Event:** an adverse event is considered to be concomitant medication-related when, in the judgment of the Investigator, it is reasonable to believe that the event is

associated with concomitant medications used in conjunction with the assigned device and is not otherwise specific to the assigned device (e.g., bleeding associated with anticoagulation medication).

***Pre-Existing Condition-Related Adverse Event:*** an adverse event is considered to be related to a pre-existing condition when, in the judgment of the Investigator, it is reasonable to believe that the event is associated with the subject's pre-existing condition and is not specific to the device or procedure. Pre-existing conditions that are aggravated or become more severe during or after the procedure should be evaluated on a case-by-case basis to determine if the event may be more appropriately classified as device-related or procedure-related.

***Unanticipated Adverse Device Effect (UADE):*** any serious adverse effect on health or safety, any life-threatening problem or death caused by, or associated with a device, if that effect, problem, or death was not previously identified in nature, severity, or degree of incidence in the application; or any other unanticipated serious problem associated with a device that relates to the rights, safety, or welfare of subjects.

Merit Medical or its designee, in cooperation with the Investigator, will assess all adverse events considered to be device-related for potential reportability to the FDA and other regulatory authorities (as applicable) as an UADE.

#### ***Events Not Considered Adverse Events***

For purposes of this study, the following events are not considered adverse events, because they are normally expected to occur in conjunction with endovascular procedures / post-procedure, or are associated with customary, standard care of subjects undergoing these procedures:

- Early post-operative pain (within 24 hours post-index procedure) at the access site and/or related to position on procedure table
- Post-anesthesia/conscious sedation emesis, nausea, or headache (within 24 hours post-index procedure)
- Chest pain without associated ECG changes
- Hematocrit decrease from baseline not associated with hemodynamic changes, remaining above 26% and not requiring transfusion
- Electrolyte imbalance without clinical sequelae following endovascular procedure, even if requiring correction
- Low grade temperature increase ( $\leq 38.3^{\circ}\text{C}/\leq 101^{\circ}\text{F}$ )
- Sinus bradycardia/tachycardia that does not require treatment or intervention
- Systolic or diastolic blood pressure changes that do not require treatment or intervention
- Minor dissections (Grade B or less) secondary to predilatation angioplasty
- Any pre-planned surgical procedures

This listing of events is intended to provide guidance to the investigational sites for purposes of adverse event reporting. The Investigator at the investigational site should utilize his/her own clinical judgment in evaluating adverse experiences and may decide that the above events should be reported as adverse events.

### **7.2 Serious Adverse Events**

A serious adverse event is defined as an adverse event that:

- Led to death,
- Led to a serious deterioration in the health of the subject, that either resulted in:
  - a life-threatening illness or injury, or
  - a permanent impairment of a body structure or a body function, or

- in-patient hospitalization or prolongation of existing hospitalization
- medical or surgical intervention to prevent life-threatening illness or injury or permanent impairment to body structure or a body function, or
- Led to fetal distress, fetal death or a congenital abnormality or birth defect.

All Serious Adverse Events will be reported throughout the study.

NOTE: Planned hospitalization for a pre-existing condition or elective cosmetic procedures, or a procedure required by the investigational plan without serious deterioration in health, is not considered a serious adverse event.

All SAEs must be reported to the IRB / EC in accordance with IRB / EC reporting requirements and institutional policies. The Investigator will note whether the adverse event was device-related or procedure-related and the severity of the event. All SAEs must be reported by the Investigator (or designee) to the Sponsor within 24 hours of knowledge of the event, or by the end of the next working day.

### **7.3 Adverse Event Reporting**

#### **7.3.1. General Reporting Requirements**

All serious and potentially device- and/or procedure-related adverse events must be recorded on the Adverse Event electronic CRF by the Investigator (or designee). The report should include: severity, duration, action taken, treatment outcome and relationship of the adverse experience to the study device, procedure, concomitant medications, pre-existing condition, (i.e., unrelated, related or relationship unknown).

In the case of serious adverse events, device-related adverse events, target lesion and access circuit interventions, and potential device malfunctions and failures, medical record documentation (e.g., procedure notes, operative notes, discharge summary, relevant progress notes, imaging, or lab studies) must be provided to the Sponsor or its designee as requested for safety adjudication by the Clinical Events Committee (CEC).

#### **7.3.2. Reporting Requirements for Serious Adverse Events**

All serious adverse events must be reported by the Investigator (or designee) to the Sponsor within 24 hours of knowledge of the event or by the end of the next working day. This may be done via phone, fax, email or electronic data capture for the clinical database.

The Investigator (or designee) shall send a written report including a narrative description of the serious adverse event to the Sponsor or their designee within five (5) working days of the initial report. This can also be in the form of the AE eCRF.

Any serious adverse events and all deaths regardless of cause may need to be reported to the IRB / EC per local IRB / EC requirements. It is the responsibility of the Investigator to inform their IRB / EC of these serious adverse events as required by their IRB / EC procedures and in conformance with FDA and local regulatory requirements. In addition, the investigator shall provide documentation of the IRB / EC report to Merit Medical or its designee.

All adverse events (AE) will be monitored from the time of enrollment through the 12-month assessment. SAEs and UADEs as well as vascular access circuit events will be monitored from the time of enrollment through the follow-up period for this trial (24 months). A description of the event, including the start date, resolution (or date of final outcome assessment) date, action taken, and the outcome should be provided, along with the Investigator's assessment of the relationship between the AE and SAE and the study treatment.

All AEs should be followed until the event is resolved or judged to be chronically stable. The clinical site should plan to provide relevant AE follow-up information to the Sponsor upon request.

The Sponsor or its designee will report all applicable serious adverse events as vigilance reports per MEDDEV 2.12.1, Rev 8 (2013) "Guidelines on a Medical Devices Vigilance System" and as clinical study reportable events per MEDDEV 2.7/3 "Clinical Investigations: Serious Adverse Event Reporting," MDCG 2020-10/1 "Guidance on safety reporting in clinical investigations" and EU MDR 2017/745 "The European Union Medical Device Regulation of 2017". The Sponsor will determine whether all of the local Investigators need to be informed immediately of an SAE or UADE, or whether this can be postponed until the next regularly scheduled study update.

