## **7.0 ADVERSE EVENTS**

All adverse events will be recorded and documented throughout the 12-month visit. Following the 12-month visit, only serious adverse events (SAE) and unanticipated adverse device effects (UADE) will be recorded and documented through the 24-month follow-up visit.

The Investigator at each participating center is ultimately responsible for reporting adverse events to the Sponsor. The adverse event electronic case report form (eCRF) provides a venue for the Investigator to record any adverse event data. The Investigator should follow all unresolved serious adverse events until the events are resolved, the subject is lost to follow-up, the subject has withdrawn consent, the subject completes the study, or the adverse event is otherwise explained.

The Sponsor shall review all adverse events for their relationship to the study device(s) and/or procedures and comparative anticipated safety event rates. The Sponsor will conduct evaluations of any unanticipated device-related event per standard operating procedures.

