### 11.1 General Duties

*(21 CFR 812.40; ISO 14155:2020 Section 9)*

The Sponsor's general duties consist of submitting the IDE application to FDA, submitting the Investigational Plan to other applicable national regulatory agencies (as applicable), obtaining FDA, other national regulatory (as applicable) and IRB / EC approvals prior to shipping the devices, selecting qualified Investigators, and shipping devices only to those qualified Investigators. As the sponsor, Merit Medical is also required to obtain signed study agreements, including documentation of financial agreements between sponsor and site/investigator, to provide the Investigators with the information necessary to

conduct the study and adequate on-site training to conduct the trial, to ensure proper clinical site monitoring, and to provide the required reports to the Investigators, IRBs / ECs, other national regulatory agencies (as applicable), and FDA.

[figure not shown]
Merit Medical is responsible for obtaining and maintaining clinical study insurance in accordance with national and local requirements and providing a copy of the insurance policy to the Investigators, IRBs / ECs, other national regulatory agencies (as applicable).

Merit Medical will be responsible for providing quality data that satisfies federal regulations and informing about serious unanticipated adverse events and deviations from the protocol. Written progress reports and a final report will be prepared in coordination with the Angiographic Core Laboratory.

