#### **11.4 Investigational Site or Study Termination**

The Sponsor reserves the right to terminate an investigational site from the Study for any of the following reasons:

- Failure to obtain Informed Consent
- Repeated failure to report Serious Adverse Events per protocol requirements
- Loss of or unaccountable device inventory
- Repeated protocol violations or safety concerns
- Repeated failure to complete Case Report Forms
- Failure to screen and enroll an adequate number of subjects

Sponsor reserves the right to terminate the study at any stage but intends to exercise this right only for valid scientific or administrative reasons and reasons related to protection of subjects. Investigators, associated IRB/ECs, and regulatory authorities, as applicable, will be notified in writing in the event of study termination. Detailed information on how enrolled subjects will be managed after termination will also be provided. Possible reasons for premature study termination include, but are not limited to, the following.

- Occurrence of unanticipated adverse device effects that present a significant or unreasonable risk to subjects enrolled in the study.
- An enrollment rate far below expectation that prejudices the conclusion of the study.
- A decision on the part of Sponsor to suspend or discontinue development of the device.

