### **12.1 Institutional review Boards / Ethics Committees**

A copy of the study protocol, proposed Informed Consent form, other written patient information and any proposed advertising material must be submitted to the IRB / EC for written approval. A copy of the written IRB / EC approval of the Protocol and Informed Consent form must be received by Merit Medical before recruitment of subjects into the study and shipment of investigational product.

The Investigator must submit and, where necessary, obtain approval from the IRB / EC as well as the FDA, for all subsequent significant protocol amendments and significant changes to the Informed Consent form. The Investigator should notify the IRB / EC of deviations from the protocol or SAEs / UADEs occurring at the site and other SAE / UADE reports received from Merit Medical in accordance with local procedures.

The Investigator will be responsible for obtaining annual IRB / EC approval and renewal throughout the duration of the study. Copies of the Investigator's reports and the IRB / EC continuance of approval must be sent to Merit Medical.

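### Section 7.3.2 lets the sponsor postpone telling investigators about an unanticipated adverse device effect (UADE), with no stated criterion or maximum delay

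*Combined protocol and SAP*

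**What the plan says.** The last paragraph of Section 7.3.2 deals with onward reporting by the sponsor. After listing the vigilance and clinical-investigation rules for SAE reports, it gives the sponsor the decision "whether all of the local Investigators need to be informed immediately of an SAE or UADE, or whether this can be postponed". The endpoint of a postponement is given only as the next routine update: "whether this can be postponed until the next regularly scheduled study update". The sentence covers SAEs and UADEs on the same terms.

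Section 7.1 defines a UADE as "any serious adverse effect on health or safety, any life-threatening problem or death caused by, or associated with a device", provided that the effect "was not previously identified in nature, severity, or degree of incidence in the application". It adds any other unanticipated serious device problem bearing on subjects' rights, safety or welfare.

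Other sections also bear on UADEs:

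- Section 7.0: "The Sponsor will conduct evaluations of any unanticipated device-related event per standard operating procedures".
- Section 11.0 commits the sponsor to report submissions under 21 CFR 812.150(b). Section 11.7, under the same citation, lists unanticipated serious device effects among the reports due to FDA.
- Section 11.1 requires the sponsor "to provide the required reports to the Investigators, IRBs / ECs, other national regulatory agencies (as applicable), and FDA".
- Section 11.4 gives as a possible reason for ending the study: "Occurrence of unanticipated adverse device effects that present a significant or unreasonable risk to subjects enrolled in the study".
- Section 12.1 expects investigators to notify their IRB / EC of events at their own site and of "other SAE / UADE reports received from Merit Medical in accordance with local procedures".

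**The concern.** Batching ordinary SAEs for a later update is reasonable in a haemodialysis population, where many will be expected or unrelated to the device. A UADE is a different kind of event. By the protocol's own definition it is serious, linked to the device, and new in nature, severity or frequency relative to the application. Section 8.2 puts prior human experience with this device at 46 subjects, so a new hazard could plausibly show itself first in this trial.

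The site that reports the event knows of it. The other centres (up to 50 in all, per the Protocol Summary) depend on the sponsor. If notice is postponed, an operator elsewhere could obtain consent and implant a stent graft without information the sponsor already holds. What is at stake is patient safety and the quality of consent, not the statistical analysis.

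**Working it through.** The plan states no figure on this point and no arithmetic applies. The check is a comparison of texts.

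**Step 1. Does the sentence really cover UADEs?** Yes. Section 7.3.2 names them, and nothing in the sentence or around it excludes them from postponement. This is a stated permission, not a missing detail.

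**Step 2. Is the permission bounded?** Section 7.3.2 gives no criterion for choosing between immediate and postponed notice. The only endpoint is the next routine update, and no interval for such updates appears in the available text.

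**Step 3. How do other reporting steps compare?**

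| Reporting step | Section | Time limit |
|---|---|---|
| Site to sponsor, SAE or UADE | 7.3.2 (SAE), Table 10 (both) | 24 hours, or close of next working day |
| Site to sponsor, device malfunction or failure | 10.5.2 | 24 hours, or close of next working day |
| Site to sponsor, IRB / EC approval withdrawn | 10.2 | 5 working days |
| Site to sponsor, major deviation | 10.5.3 | 5 working days |
| Sponsor to all investigators, UADE | 7.3.2 | none stated; may wait for the next update |

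The steps into the sponsor have limits. The step from the sponsor out to the other sites has none.

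**Step 4. Does another section supply the limit?**

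- 7.0 requires an evaluation under standard operating procedures. It gives no deadline and does not mention notice to investigators.
- 11.0 and 11.7 cite 21 CFR 812.150(b). The documents do not reproduce any deadline from it, and the UADE item in 11.7 is about reports to FDA.
- 11.1 states a duty to give investigators and IRBs / ECs the required reports, and to inform about serious unanticipated events. It gives no deadline, and the duty to inform names no recipient.
- 11.4 promises written notice to investigators, but only if the study is terminated.
- 12.1 assumes that sponsor reports reach investigators. It does not say when.

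None of these sections states a deadline for telling investigators, and none says that it overrides 7.3.2.

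**Step 5. What follows?** 7.3.2 is the specific rule that safety staff would apply. The general duties in 11.0, 11.1 and 11.7 point towards prompt reporting, but the text does not say how they and the discretion in 7.3.2 fit together. Under 12.1, a postponed notice can also delay what investigators pass on to their IRB / EC, although that is not the only route to those committees.

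**The case against.** The strongest reply is that 7.3.2 only gives the sponsor a choice. It neither requires nor presumes delay for UADEs, and it can be read as operating within the duties in 11.0 and 11.1. Since 11.1 sets no time limit, there is no flat contradiction with it. UADEs also have their own handling elsewhere: evaluation (7.0), assessment for reportability to regulators (7.1), reports to FDA (11.7) and a role as grounds for termination (11.4). IRBs / ECs have other sources too: directly from the sponsor under 11.1, and from the site where the event occurred under Table 10. Finally, Sections 10.4, 11.3, 12.8 and 12.9 do not appear in the public copy, and the procedures cited in 7.0 are not available, so further safeguards may exist.

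Most of this stands, and it limits the point. These duties make harm less likely, and the absence of a deadline can be asserted only for the text that is available. They do not remove the difficulty: the permission to postpone is explicit, it includes UADEs, and nothing available qualifies it. If a missing section does hold a safeguard, 7.3.2 would still have to be reconciled with it.

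Two stronger readings are tempting and are not supported. A reader might infer that sites will keep implanting in ignorance of a new hazard; the documents show only that they could. A reader might also divide planned implants by the enrolment period and multiply by an assumed update interval. The interval is not given, and the annual minimum in Table 10 cannot stand in for it, because that entry concerns progress reports required by the local IRB / EC.

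**Conclusion.** The point holds as a gap in safety communication. Section 7.3.2 permits postponed notice of a UADE to investigators, without a stated criterion or maximum delay, for a class of event that Section 7.1 defines as serious and new. This fits poorly with the commitments in 11.0, 11.1 and 11.7, and the sections should be reconciled.

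Its size cannot be expressed as a number of subjects. It depends on whether a UADE occurs, whether the sponsor chooses to postpone, and how long the update interval is; the documents settle none of these. The conclusion does not depend on the content of the cited regulation, so no breach of it is asserted. It rests on the wording of 7.3.2 and on no available section qualifying that wording. Endpoints, sample size, error control and analysis are untouched. The change is worth making because it is cheap and concerns the safety of subjects.

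**What to change.** In Section 7.3.2, limit the option to postpone to SAEs that are not UADEs. Add that UADE notices to all investigators and all reviewing IRBs / ECs follow the 21 CFR 812.150(b) reporting commitment already made in 11.0 and 11.7, and do not wait for the next routine update. A cross-reference to 11.1 would make clear that the general duty governs.

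The cost is about one sentence of text and an occasional extra safety letter. There is no statistical cost. If the sponsor already sends UADE notices promptly, the amendment only brings the wording into line with practice.
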